#### **Hypothesis Testing:**

The null and alternative hypotheses for no difference of Test relative to Control are as follows:

$$H_0: OR = 1$$
$$H_A: OR \neq 1,$$

where  $OR$  is odds ratio of having a Grade 2 or higher corneal staining in the Test group over the Control group.

Comparison between the Test and Control will be conducted at each follow-up visit and across all visits. The test for no difference will be based on the estimated OR and corresponding 95% confidence interval from the final model. The null hypothesis will be rejected in favor of the alternative if 1 does not fall within the 95% confidence interval of OR. The corneal staining analysis will be conducted on the Safety Population.

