#### **Secondary hypotheses:**

1. The proportion of eyes with Grade 2 or higher corneal staining in the Test group will be no different to that in the Control group.
2. The change in overall quality of vision from baseline at 7-Day and 30-Day follow-up of the Test eye drops will be no different to that of the Control eye drops.
3. The proportion of eyes with reported ocular symptoms in the Test group will be no different to that in the Control group.
4. The Test eye drops will be non-inferior to the Control eye drops with respect to change in ocular comfort from baseline at 7-Day follow-up. A non-inferiority margin of -20 point ocular comfort VAS scale will be used.

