#### **14.6. Secondary Analysis**

##### Corneal Staining (Grade 2 or higher):

Corneal staining response using FDA grading scale (i.e. Grade 0 = None, Grade 1 = Trace, Grade 2 = Mild, Grade 3 = Moderate and Grade 4 = Severe) will be first categorized into a binary outcome as 1 if any grade 2 or higher corneal staining otherwise 0. Events occurring during an unscheduled visit will be counted in the subsequent visit. For example, if a Grade 2 corneal staining was reported at an unscheduled visit between Visit 1 and Visit 2, it would be counted in Visit 2. Eyes with multiple reports will be counted only once at each visit for the analysis purpose. The binary outcome will be then analyzed using a generalized linear mixed model for binary data. The regression model will include treatment group (Test, Control), time (0, 7-Day and 30-Day) and group by time interaction as fixed effect factors; and investigational site and subject as random effects (G-side). Baseline values, age and gender will be included in the model as fixed covariates when appropriate. The correlation between measurements from the same subject/eye across time will be modeled using UN variance-covariance matrix (R-side). If the estimation algorithm does not converge, then a compound symmetry structure (CS) will be used. The Kenward and Roger method will be used to calculate the denominator degree of freedom.

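### Secondary hypotheses 1–3 claim no difference but get only difference tests without a margin, and the pooled staining odds ratio does not clearly exclude baseline

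*Combined protocol and SAP*

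**What the plan says.** Section 2.3 lists four secondary hypotheses. The first reads "The proportion of eyes with Grade 2 or higher corneal staining in the Test group will be no different" from Control. The third reads "The proportion of eyes with reported ocular symptoms in the Test group will be no different to that in the Control group". The second says the same of change in quality of vision at Day 7 and Day 30. The fourth is of another kind: "The Test eye drops will be non-inferior to the Control eye drops with respect to change in ocular comfort from baseline at 7-Day follow-up", with a margin of -20 VAS points.

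Section 14.6 tests staining with a null odds ratio (OR) of 1 against any other value: "The test for no difference will be based on the estimated OR and corresponding 95% confidence interval from the final model", and "The null hypothesis will be rejected in favor of the alternative if 1 does not fall within the 95% confidence interval of OR". Symptoms use the same method, and vision gets t-tests on least-square mean differences. None of the three has a margin or a criterion for concluding sameness. Section 14.2 sizes the trial for comfort only.

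For the staining model, "The regression model will include treatment group (Test, Control), time (0, 7-Day and 30-Day) and group by time interaction as fixed effect factors". The contrasts are then set by "Comparison between the Test and Control will be conducted at each follow-up visit and across all visits".

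**The concern.** In hypotheses 1–3 the claim to be supported is the null hypothesis of its own test. Failing to reject a null does not establish it. The authors separate the two kinds of claim elsewhere: for Day-30 comfort the desired conclusion is the alternative, and hypothesis 4 carries a margin.

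Staining and symptoms are the between-group safety comparisons for a new product, in a trial meant to support European registration. If a non-significant OR is taken as confirming the hypothesis, a small trial could be reported as showing sameness when its interval still contains a material increase.

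The second issue concerns the pooled OR. Visit 1 staining is graded at steps 1.11–1.12 of section 7.2, before randomization (1.15) and the first drop (1.16). Its expected OR is therefore 1, and averaging it in pulls the overall OR towards 1.

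**Working it through.** **1. The plan's own figure.** With a two-sample noncentral t, margin 20, true difference 0, SD 35 and one-sided 0.025, power is 84.37% at 55 per arm and 85.02% at 56. The stated 56 reproduces. No such calculation exists for staining, vision or symptoms.

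**2. Staining at one visit.** From section 4.3: 60 subjects per arm, so 120 eyes. Assumed, because the documents give none: control rates of 5%, 10% and 20%, and a between-eye correlation (ICC) of 0.4 or 0.7.

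- Effective eyes per arm: n = 120/(1 + ICC) = 85.7 or 70.6.
- SE(ln OR) = √{[1/(p₁q₁) + 1/(p₂q₂)]/n}.
- Power ≈ Φ(ln OR/SE − 1.96). Upper limit at equal rates = exp(1.96 × SE).
- Example, 10% to 20%, ICC 0.4: ln 2.25 = 0.811; SE = √[(11.11 + 6.25)/85.7] = 0.450; power = Φ(1.80 − 1.96) = 44%. With both arms at 10%: SE = √(2 × 11.11/85.7) = 0.509, and the upper limit is exp(0.998) = 2.71.

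| Control → Test | OR for a doubling | Power, one visit | Upper 95% limit, equal rates |
|---|---|---|---|
| 5% → 10% | 2.11 | 20–23% | 4.0–4.5 |
| 10% → 20% | 2.25 | 37–44% | 2.7–3.0 |
| 20% → 40% | 2.67 | 72–80% | 2.1–2.3 |

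Simulated correlated eye data with cluster-robust log-ORs agree broadly. Power is 14–20% and 36–44% in the first two rows, and the median upper limits are 4.0–4.7 and 2.7–3.1. A logistic mixed model with a random subject intercept, nearer to the planned model, gives 23–26% and 43–53%. Its type I error was 4–9%, so those powers are slightly flattered.

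**3. Symptoms.** With an assumed control rate of 30–50% and ICC 0.7 or 0.9, a 15-point rise has 38–45% power at one visit (cluster-robust simulation).

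**4. Vision.** 56 per arm. The SD is borrowed from comfort: 25.3 (the 2.53 in section 14.2, rescaled to 0–100) or 35.

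- Half-width of the 95% CI = t(0.975, 110) × SD × √(2/56).
- SD 25.3: 1.982 × 25.3 × 0.189 = 9.5 points. SD 35: 1.982 × 35 × 0.189 = 13.1 points.
- Power for a true 10-point difference (noncentral t): 55% and 32%.

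**5. Pooled staining OR.** With equal visit weights, a log-OR of 0 at time 0 and L at both follow-ups, the average is 2L/3. An OR of 2 becomes exp(⅔ ln 2) = 1.59, and 3 becomes exp(⅔ ln 3) = 2.08. In the cluster-robust simulation, power of the pooled test falls from 24–36% to 13–22% (5% to 10%) and from 51–66% to 28–41% (10% to 20%). The two visit-specific tests do not change. The chance that at least one of the three staining tests rejects falls by only about 1–4 points.

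**The case against.** The strongest reply is that the harmful step is not in the plan. Section 14.6 says when the null is rejected, and never says what follows if it is not. The primary test, by contrast, spells out its positive conclusion. Hypotheses 1–3 can be read as loosely worded nulls of ordinary difference tests. A reader might infer that the sponsor has committed to reporting non-significance as sameness; the documents do not say so. What remains is that they are listed as hypotheses, beside a properly framed fourth, with no test that could support them.

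A reader might also infer that any non-significant staining result is compatible with a doubling. That depends on the rate. At 20%, equal observed rates would exclude it (upper limit 2.1–2.3 against an OR of 2.67), although a non-significant result nearer the boundary might not. Such a rate cannot be ruled out: section 3.2 enrols people with dryness symptoms and/or tear use, and section 3.3 excludes only Grade 3 or above.

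A third tempting reading is that the pooled OR would hide harm. The phrase about all visits may mean only the follow-up visits just named, and the visit-specific ORs are intact. The stand-alone SAP promised in section 14.1 was not available and may define the contrast.

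It is also fair that the OR and its interval are already planned, that sizing for the primary endpoint alone is not an error, and that safety is followed through slit lamp findings, adverse events and discontinuations as well.

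**Conclusion.** The point holds as a minor one. Followed as written, the plan cannot support hypotheses 1–3, because it pairs claims of no difference with difference tests that have no margin. At assumed control staining rates of 5–10%, one-visit power for a doubling is roughly 14–44% by the cluster-robust calculation, and the upper limit at equal true rates is about 2.7–4.7. A non-significant result would then often fail to exclude a doubling; at 20% that concern largely recedes. For vision the interval extends 9.5–13.1 points either side, if the comfort SDs carry over.

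The pooled-OR issue is an ambiguity. The dilution from 2 to 1.59 rests on the literal reading, equal visit weights and a baseline OR of 1. It affects the overall OR that would be reported far more than the chance that some test detects harm. No success criterion and no primary conclusion changes.

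**What to change.** In sections 2.3 and 14.6:

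- Restate hypotheses 1–3 as between-group estimates with 95% confidence intervals: the OR for staining and symptoms, as already planned, and the least-square mean difference for vision, where only t-tests are named and the interval should be added.
- State that a non-significant result will not be reported as no difference or as equivalence.
- Define the overall OR as the average of the Day-7 and Day-30 log-ORs only.

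The cost is wording and one contrast statement, with no new data, visits or subjects. The sponsor gives up an easy statement that the products do not differ on these endpoints.

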**Overall Quality of Vision Score:**

Overall quality of vision will be analyzed using the same statistical model described in the primary analysis. Comparisons between Test and Control will be carried using t-tests on least square mean differences of change in quality of vision from baseline at 7-Day and 30-Day follow-up. The overall quality of vision analysis will be conducted on the Per-Protocol Population.

**Subject reported Ocular symptoms (yes/No)**

Reported ocular symptoms, problems or complaints (0 = No, 1 = Yes) at any visit will be analyzed using the same method described above for corneal staining. The reported ocular analysis will be conducted on the Safety Population.

**14.7. Other Exploratory Analyses**

No exploratory analyses are planned for this study. Further analysis will be conducted at the discretion of the study responsible clinician at the end of the study if necessary.

**14.8. Interim Analysis**

No interim analysis is planned in this study.

**14.9. Procedure for Handling Missing Data and Drop-Outs**

Missing or spurious values will not be imputed as the number of missing values is expected to be low. The count of observed values will be included in the summary tables and listings.

Subject dropout is expected to be one of the main reasons of missing data in this clinical trial. Past clinical trials don't provide the evidence that subject dropout is systematic or not-at-random. To evaluate the impact of missing data, a sensitivity analysis will be conducted using multiple imputation methods.

**14.10. Procedure for Reporting Deviations from Statistical Plan**

The analysis will be conducted according to that specified in the above sections. There are no known reasons for which it is planned to deviate from these analysis methods. If for any reason a change is made, the change will be documented in the study report along with a justification for the change.

**15. DATA HANDLING AND RECORD KEEPING/ARCHIVING**

**15.1. Electronic Case Report Form/Data Collection**

The data for this study will be captured on electronic case report forms (eCRFs) using an EDC system (Bioclinica). An authorized data originator will enter study data into the eCRFs using the EDC system. Data collected on equipment that is not captured in EDC

will be formatted to the specification of the JJV database manager and sent to JJV for analysis.

External Date Sources for this study include: Not Applicable

The clinical data will be recorded on dedicated eCRFs specifically designed to match the study procedures for each visit. Once completed, the eCRFs will be reviewed for accuracy and completeness and signed by the Investigator. The sponsor or sponsor's representatives will be authorized to gain access to the subject recordation for the purposes of monitoring and auditing the study.

Edit checks, electronic queries, and audit trails are built into the system to ensure accurate and complete data collection. Data will be transmitted from the clinical site to a secure central database as forms are completed or updated, ensuring information accuracy, security, and confidentiality. After the final database lock, the Investigator will be provided with Individual Patient Profiles (IPP) including the full audit trail on electronic media in PDF format for all of the study data. The IPP must be retained in the study files as a certified copy of the source data for the study.

The content and structure of the eCRFs are compliant with ISO14155:2011.

## **15.2. Subject Record**

At a minimum, subject record should be available for the following:

- subject identification
- eligibility
- study identification
- study discussion
- provision of and date of informed consent
- visit dates
- results of safety and efficacy parameters as required by the protocol
- a record of all adverse events
- follow-up of adverse events
- medical history and concomitant medication
- test article receipt/dispensing/return records
- date of study completion
- reason for early discontinuation of test article or withdrawal from the study, if applicable

The subject record is the eCRF or an external record. The author of an entry in the subject record must be identifiable. The first point of entry is considered to be the source record.

Adverse event notes must be reviewed and initialed by the Investigator.

# **16. DATA MANAGEMENT**

## **16.1. Access to Source Data/Document**

The Investigator/Institution will permit trial-related monitoring, audits, IEC/IRB review and regulatory inspection(s) by providing direct access to source data/documents. Should

the clinical site be contacted for an audit by an IEC/IRB or regulatory authority, JJV must be contacted and notified in writing within 24 hours.

### **16.2. Confidentiality of Information**

Information concerning the investigational product and patent application processes, scientific data or other pertinent information is confidential and remains the property of JJV. The Investigator may use this information for the purposes of the study only. It is understood by the Investigator that JJV will use information developed in this clinical study in connection with the development of the investigational product and therefore may disclose it as required to other clinical investigators and to regulatory agencies. In order to allow the use of the information derived from this clinical study, the Investigator understands that he/she has an obligation to provide complete test results and all data developed during this study to the Sponsor.

### **16.3. Data Quality Assurance**

Steps will be taken to ensure the accuracy and reliability of data, include the selection of qualified investigators and appropriate clinical sites and review of protocol procedures with the Principal Investigator. The Principal Investigator, in turn, must ensure that all Sub-Investigators and clinical site personnel are familiar with the protocol and all study-specific procedures and have appropriate knowledge of the study article.

Training on case report form completion will be provided to clinical site personnel before the start of the study. The Sponsor will review case report forms for accuracy and completeness remotely during the conduct of the study, during monitoring visits, and after transmission to data management. Any data discrepancies will be resolved with the Investigator or designee, as appropriate.

Quality Assurance representatives from JJV may visit clinical sites to review data produced during the study and to access compliance with applicable regulations pertaining to the conduct of clinical trials. The clinical sites will provide direct access to study-related source data/documents and reports for the purpose of monitoring and auditing by JJV and for inspection by local and regulatory authorities.

## **17. MONITORING**

The study monitors will maintain close contact with the Principal Investigator and the Investigator's designated clinical site personnel. The monitor's responsibilities will include:

- Ensuring that the investigation is being conducted according to the protocol, any subsequent amendments, and regulatory requirements are maintained
- Ensuring the rights and wellbeing of subjects are protected
- Ensuring adequate resources, including facilities, laboratories, equipment, and qualified clinical site personnel
- Ensuring that protocol deviations are documented with corrective action plans, as applicable
- Ensuring that the clinical site has sufficient test article and supplies
- Clarifying questions regarding the study
- Resolving study issues or problems that may arise

- Reviewing of study records and source documentation verification in accordance with the monitoring plan

## **18. ETHICAL AND REGULATORY ASPECTS**

### **18.1. Study-Specific Design Considerations**

Potential subjects will be fully informed of the risks and requirements of the study and, during the study, subjects will be given any new information that may affect their decision to continue participation. Subjects will be told that their consent to participate in the study is voluntary and may be withdrawn at any time with no reason given and without penalty or loss of benefits to which they would otherwise be entitled. Only subjects who are fully able to understand the risks, benefits, and potential adverse events of the study, and provide their consent voluntarily will be enrolled.

### **18.2. Investigator Responsibility**

The Principal Investigator is responsible for ensuring that the clinical study is performed in accordance with the signed agreement, the investigational plan, Section 4 of the ICH E6 guidelines on Good Clinical Practice (GCP), and applicable regulatory requirements. GCP is an international ethical and scientific quality standard for designing, conducting, recording, and reporting studies that involve the participation of human subjects. Compliance with this standard provides public assurance that the rights, safety, and well-being of study subjects are protected, consistent with the principles of the Declaration of Helsinki 64th WMA General Assembly 2013 and that the clinical study data are credible. The Investigator must maintain clinical study files in accordance with Section 8 of the ICH E6 guidelines on Good Clinical Practice (GCP), and applicable regulatory requirements.

### **18.3. Independent Ethics Committee or Institutional Review Board (IEC/IRB)**

Before the start of the study, the Investigator (or Sponsor when applicable) will provide the IEC/IRB with current and complete copies of the following documents (where applicable):

- Final protocol and, if applicable, amendments
- Sponsor-approved informed consent form (and any other written materials to be provided to the subjects)
- Investigator's Brochure (or equivalent information) and amendments
- Sponsor-approved subject recruitment materials
- Information on compensation for study-related injuries or payment to subjects for participation in the study
- Investigator's curriculum vitae, clinical licenses, or equivalent information (unless not required, as documented by IEC/IRB)
- Information regarding funding, name of the Sponsor, institutional affiliations, other potential conflicts of interest, and incentives for subjects
- Any other documents that the IEC/IRB requests to fulfill its obligation

This study will be undertaken only after IEC/IRB has given full approval of the final protocol, amendments (if any), the informed consent form, applicable recruiting materials, and subject compensation programs, and the Sponsor has received a copy of this approval. This approval letter must be dated and must clearly identify the documents being approved.

During the study, the Investigator (or Sponsor when applicable) will send the following documents to the IEC/IRB for their review and approval, where appropriate:

- Protocol amendments
- Revision(s) to informed consent form and any other written materials to be provided to subjects
- If applicable, new or revised subject recruitment materials approved by the Sponsor
- Revisions to compensation for study-related injuries or payment to subjects for participation in the study
- Investigator's Brochure amendments or new edition(s)
- Summaries of the status of the study (at least annually or at intervals stipulated in guidelines of the IEC/IRB)
- Reports of adverse events that are serious, unanticipated, and associated with the test articles, according to the IRB's requirements
- New information that may adversely affect the safety of the subjects or the conduct of the study
- Major protocol deviations as required by the IEC/IRB
- Report of deaths of subjects under the Investigator's care
- Notification if a new Investigator is responsible for the study at the clinical site
- Any other requirements of the IEC/IRB

For protocol amendments that increase subject risk, the amendment and applicable informed consent form revisions must be submitted promptly to the IEC/IRB for review and approval before implementation of the change(s).

At least once a year, the IEC/IRB will review and reapprove this clinical study. This request should be documented in writing.

At the end of the study, the Investigator (or Sponsor where required) will notify the IEC/IRB about the study completion. Documentation of this notification must be retained at the clinical site and a copy provided to the CRO or Sponsor as applicable.

#### **18.4. Informed Consent**

Each subject must give written consent according to local requirements after the nature of the study has been fully explained. The consent form must be signed before performance of any study-related activity. The consent form that is used must be approved by both the Sponsor and by the reviewing IEC/IRB. The informed consent is in accordance with principles that originated in the Declaration of Helsinki, current ICH and ISO 14155 guidelines, applicable regulatory requirements, and Sponsor Policy.

Before entry into the study, the Investigator or an authorized member of the clinical site personnel must explain to potential subject the aims, methods, reasonably anticipated benefits, and potential hazards of the study, and any discomfort it may entail. Subjects will be informed that their participation is voluntary and that they may withdraw consent to participate at any time.

The subject will be given sufficient time to read the informed consent form and the opportunity to ask questions. After this explanation and before entry into the study, consent should be appropriately recorded by means of the subject's dated signature. After having obtained the consent, a copy of the informed consent form must be given to the subject.

